4. AIMS & OBJECTIVES

The aim of the cohort study is to establish a rolling cohort of patients with mesothelioma, in order to collect longitudinal data on the natural history of MPM, create a biobank of biological samples, and provide a resource for future TwiCs.

Specific objectives include the collection of longitudinal data across multiple domains including clinical, biochemical, biometric and psychological parameters. This data will provide information on the natural history of MPM and will allow comparison of outcomes in participants who undergo different management pathways. The collection and analysis of biological samples, including blood and pleural fluid, will allow investigation of novel biomarkers and exploration of other clinical and biochemical factors that influence outcome. Finally, longitudinal data collected in the cohort will provide control group data for TwiCs conducted within the cohort.

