5.6 Sample size & recruitment targets

The sample size necessary to detect a difference in survival between different patient groups is 266 participants per group, i.e. 532 in total. Setting the recruitment target at 700 allows for approximately 20% withdrawals from the study, incomplete data and loss to follow up following initial enrolment. This calculation is based on the survival outcomes from previous chemotherapy trials in mesothelioma, in which chemotherapy increased 1 year survival from 38% to 50%.⁹ With alpha of 0.05, a cohort of this size will provide 80% power to detect a similar difference in 1 year survival, based on an individual patient characteristics (split at the median) or treatment received (binary yes/no data).

NBT Pleural Service diagnoses approximately 50 new cases of MPM each year, whilst ORTU sees 30. It is anticipated that 90% of these people will be eligible to participate in the cohort.

Observational studies tend to have higher recruitment rates than interventional trials.¹⁶ NBT Pleural Service has been recruiting patients with pleural disease to an observational study since 2008 (Investigating Pleural Disease, UKCRN 8960, REC reference 08/H0102/11), in which 80% of eligible patients screened consented to participate. Assuming similar rates for this cohort, approximately 50 patients will be recruited each year from the two lead centres. With these recruitment rates the study will recruit 700 participants in approximately 14 years. However, it is anticipated that after the first 100 participants have been recruited, additional study centres will be invited to join the cohort, thus expediting recruitment and ensuring it is completed within 10 years.

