6.2 Follow up assessments

Study assessments will be undertaken when the participant attends for review as part of standard clinical care. This should happen every 3 months as a minimum. Some participants will require more frequent follow-up for clinical reasons and will therefore undergo more frequent assessment. Participants who are eligible for participation in future TwiCs may be invited to attend more regular study assessments at one of the study centres, in accordance with the follow up schedule for that specific TwiC.

[figure not shown]
At each visit participants will undergo clinical assessment, including review of symptoms, medication history, oncological treatment received, details of any pain interventions, any engagement with Specialist Palliative Care teams and change in clinical status. Blood tests will be taken for FBC, U&E, LFT, CRP and random glucose,. A sample of blood will be taken for storage. Pleural fluid drainage diaries will be reviewed and documented. Participants who have an indwelling pleural catheter in situ or who are undergoing pleural aspiration for clinical reasons will have pleural fluid biochemistry tested and have a sample of pleural fluid taken for storage. Participants will complete PROMS for QoL and VAS scores for chest pain, breathlessness and sweats. Intermittently participants will be invited to complete daily VAS scores from home and will be provided with a VAS booklet to complete.

Radiological imaging, including CXR, CT thorax and bedside TUS will be undertaken at the discretion of the clinician, based on clinical need. It is anticipated that participants will have a CXR, TUS or both at every clinic appointment as part of routine care. It is expected that participants will have a CT scan every 6 months as a minimum for routine clinical care. If a participant has more frequent CT scans, for clinical reasons, these images will be collected as part of the study.

At each follow up assessment, cohort participants will be assessed for their eligibility to participate in any trials (TwiCs) that are currently underway within the cohort. Any participant who meets the eligibility criteria for a TwiC will be provided with a PIS for that trial and given the opportunity to discuss it with a member of the trial team. As part of the screening process, additional blood samples or investigations may be undertaken to determine or confirm eligibility for specific trials. These activities are deemed ASSESS-meso

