7. STATISTICAL ANALYSIS PLAN

We will use multiple linear regression to compare continuous outcomes; logistic regression to compare dichotomous outcomes and Cox’s proportional hazards to compare survival between different groups controlling for confounding factors. We will use random effects models or robust estimates to allow for clustering between centres. Outcomes with repeat measurements will be analysed using regression modelling with adjustment for baseline values.

The sensitivity, specificity, NPV and PPV for predicting disease progression will be assessed at established cut-off levels for serum and pleural fluid biomarkers, cytokines, immune profile, receptor status and epigenetic markers. Receiver operator characteristic curves will be drawn. The gold standard for disease progression will be confirmation of progressive disease made at the regional mesothelioma MDT meeting.

An interim analysis will be undertaken once recruitment reaches 25% of target (i.e. n=175), describing the baseline characteristics of participants, and evaluating generalisability of the cohort population with comparison to existing real-world cohorts, e.g. National Lung Cancer Audit Mesothelioma Report.

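### Survival is grouped by treatment received, yes or no, although treatment can start after enrolment; coded from time zero this creates immortal-time bias that can reach the design effect

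*Protocol*

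**What the plan says.** - **Objective (Section 4).** The longitudinal data "will allow comparison of outcomes in participants who undergo different management pathways".
- **Grouping and size (Section 5.6).** The requirement is "266 participants per group, i.e. 532 in total", taken from earlier trials in which "chemotherapy increased 1 year survival from 38% to 50" per cent. "With alpha of 0.05, a cohort of this size will provide 80% power to detect a similar difference in 1 year survival", with groups formed "based on an individual patient characteristics (split at the median) or treatment received (binary yes/no data").
- **Analysis (Section 7).** The plan uses Cox's "proportional hazards to compare survival between different groups controlling for confounding factors". It names no time origin, time-dependent exposure, landmark or delayed entry.
- **When treatment is recorded (Sections 6.2 and 6.4).** "At each visit participants will undergo clinical assessment, including review of symptoms, medication history, oncological treatment received". The schedule of assessments lists oncological treatment history at baseline, at follow-up and at telephone assessments.
- **When participants enter (Section 5.4).** Newly diagnosed patients are screened at the weekly MDT and approached at their next clinic appointment, with no limit on the time from diagnosis to enrolment. Treatment may therefore start before or after entry.

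**The concern.** A yes/no group built from treatment that begins during follow-up is defined by the future. Nobody can enter the treated group without living until treatment starts, so the waiting time before the start is event-free by construction and is credited to treatment. Participants who die while waiting are counted as untreated. The error lies in how person-time is allocated, so adjusting for age, histology or performance status leaves it in place.

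Comparing management pathways is a stated objective, and median survival is about a year, so a wait of weeks to months is a material share of follow-up. An inactive treatment would appear to prolong life. The 38% and 50% in Section 5.6 come from a randomised comparison, where groups are fixed at allocation and this problem does not arise.

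**Working it through.** **Inputs from the protocol.** 1-year survival 38% v 50%, alpha 0.05, power 80%, 266 per group (Section 5.6); median survival about 12 months (Section 6.9), range 8 to 14 (Section 3.1); most patients do not receive chemotherapy (Section 3.4).

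**Assumptions (not in the protocol).** Exponential survival from enrolment; no true treatment effect; share p intended for treatment 30-60%; delay to treatment varied.

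**1. The plan's own figure.** Two proportions, two-sided, mean 0.44:
- Pooled: [1.96√(2×0.44×0.56) + 0.8416√(0.38×0.62 + 0.50×0.50)]² / 0.12² = (1.376 + 0.586)² / 0.0144 = 267.4, so 268.
- Unpooled: (1.96 + 0.8416)² × 0.4856 / 0.0144 = 264.7, so 265.

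The stated 266 is reproduced. As a hazard ratio the effect is ln 0.50 / ln 0.38 = 0.716. The formula takes group membership as known at time zero.

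**2. Bias with a single delay d.** With S(t) = 0.5^(t/12), a participant is treated only if intended for treatment and alive at d.
- 1-year survival, treated: S(12)/S(d).
- 1-year survival, untreated: (1−p)S(12) / (1−pS(d)).
- The true value in both groups is 50%.

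Example, d = 3 and p = 0.5: S(3) = 0.8409. Treated 0.5/0.8409 = 59.5%; untreated 0.25/(1−0.4204) = 43.1%; spurious gap 16.3 points. Mean survival overall is 12/ln 2 = 17.31 months. For the treated it is 3 + 17.31 = 20.31, and for the untreated (17.31 − 0.4204×20.31)/0.5796 = 15.14. The death-rate ratio is 15.14/20.31 = 0.75.

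| Delay (months) | Gap, p = 30% | Gap, p = 50% | Rate ratio, 30% / 50% |
|---|---|---|---|
| 1 | 4.1 | 5.6 | 0.92 / 0.90 |
| 2 | 8.4 | 11.0 | 0.86 / 0.81 |
| 3 | 12.6 | 16.3 | 0.80 / 0.75 |
| 4 | 17.1 | 21.6 | 0.75 / 0.69 |

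Solving for 12 points gives a delay of about 2.2 months (p = 50%) or 2.9 months (p = 30%). The full-follow-up ratio falls to 0.716 only at about 3.5 and 5 months respectively.

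Other medians at a 3-month delay:
- Median 8, p = 0.5: 0.3536/0.7711 − 0.1768/0.6145 = 45.9% − 28.8% = 17.1 points.
- Median 14, p = 0.3: 0.5520/0.8620 − 0.3864/0.7414 = 64.0% − 52.1% = 11.9 points.

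**3. Starts spread over a window.** Replace S(d) by its average over the window, with hazard ln 2/12 = 0.05776.
- 0-2 months: average (1 − 0.8909)/0.1155 = 0.9444. Treated 52.9%; untreated 48.8% (p = 30%) to 46.1% (p = 60%). Gap 4.1 to 6.8 points; simulated hazard ratio about 0.92 to 0.88.
- 1-4 months: average (0.9439 − 0.7937)/0.1733 = 0.8666. Treated 57.7%; untreated 47.3% to 41.7%. Gap 10.4 to 16.0 points; simulated hazard ratio about 0.83 to 0.75.

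**4. Effect on the test.** Simulated with no effect, n = 532, p = 50%, median 12 months, 400 runs. Yes/no coding from time zero rejects in 31%, 66%, 92% and 99% of runs for delays of 1, 2, 3 and 4 months. Time-dependent coding gives hazard ratios of 0.99-1.00 and rejects in 4.5-7%.

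**The case against.** The attacked phrase belongs to a power statement: it says which two-group contrasts the cohort could detect, not how exposure enters the model. Section 7 does not say that treatment will be a fixed covariate from enrolment. Cox regression accepts time-dependent exposure, and a separate SAP could specify it. Treatment history is also taken at baseline, and anyone already treated at entry contributes no immortal time if the clock starts at enrolment. Every delay used above is assumed. The upper share is generous too: 60% intended with starts at 1-4 months means 0.60 × 0.8666 = 52% treated, although Section 3.4 says most patients do not receive chemotherapy.

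Much of this stands. A reader might infer that the bias is bound to equal the design effect; the protocol gives no delay that would support that, and with starts at 0-2 months it is about a third to a little over half of 12 points. A reader might also infer that the protocol commits to ever/never coding from enrolment; it leaves the time origin and the timing of exposure open. Nor does the two-group calculation have to be abandoned, since it works as an approximation once status is fixed at a defined time.

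What does not fall away is that Section 5.6 names a grouping and Section 7 pairs it with a survival comparison whose only stated safeguard is confounder adjustment. Followed as written, with treatment starting during follow-up, that gives the bias. A later SAP would have to qualify the wording of Section 5.6 to avoid it.

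**Conclusion.** The point holds in a bounded form. Coding treatment that starts after time zero as yes/no from time zero biases the survival comparison in favour of treatment, and the planned adjustment does not correct it.

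The size depends on a delay and a treated share that the protocol does not give. On the 1-year scale used in Section 5.6, the spurious difference is about 4-7 points for starts at 0-2 months and about 10-16 points for starts at 1-4 months. It can therefore match the 12-point design effect when treatment begins about 2-3 months or more after time zero. On the full-follow-up hazard ratio scale the bias is milder and needs a longer delay to reach 0.716. These figures rest on exponential survival, a 12-month median, 30-60% intended for treatment and every treated participant starting after entry; those already treated at enrolment would dilute them. Comparisons by a baseline characteristic split at the median are unaffected.

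**What to change.** **Section 7.** Define time zero. Enter treatment started after it as a time-dependent covariate in the Cox model, unexposed until the start date and exposed from then on. If time runs from diagnosis, allow for delayed entry, because enrolment may come at any interval after diagnosis. For the 1-year comparison, use a landmark analysis: participants alive at a prespecified time, classified by treatment begun by then.

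**Section 5.6.** Keep the two-group calculation as an approximation, but state that yes/no treatment status is fixed at time zero or at the landmark, not by treatment ever received.

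**Data.** Record treatment start dates within the treatment history already collected; Sections 6.2 and 6.4 list the history without naming dates.

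**Cost.** Wording plus one date field, with no change to recruitment or visits. The landmark analysis drops early deaths: at 3 months 1 − 0.5^(3/12) = 16% of participants with a 12-month median, or 1 − 0.5^(3/8) = 23% with an 8-month median. It is somewhat less precise and describes only those who survive to the landmark.

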5.7 Co-enrolment guidelines

One of the primary aims of the cohort study is to establish a resource from which future TwiCs can be recruited. Therefore, participants in the cohort will be permitted to participate in other research studies and trials concurrent to their participation in the cohort. It is likely that this research will be co-ordinated and managed by either NBT or ORTU Pleural Teams, at least initially, but it is acknowledged that some patients may be invited to participate in oncological treatment trials or trials co-ordinated by other teams. There is no restriction on participation in any of these trials, provided the CI is informed at the time of co-enrolment, and is comfortable that there will be no conflict between studies. Co-enrolment will be documented on individual CRFs.

6. STUDY ASSESSMENTS

6.1 Baseline assessments

Having provided written or witnessed verbal informed consent to participate in the cohort, participants will undergo baseline assessment. This will include documentation of patient demographics (including whether or not they are living alone, their postcode, and alcohol history), disease characteristics, co-morbidities and medication history. Patient-reported outcome measures (PROMs) will be collected, specifically the EuroQol 5D health questionnaire, EQ-5D-5L and symptom scores for breathlessness, chest pain and sweats. For symptom scores, participants will be asked to assess the severity of the relevant symptom over the preceding 24 hour period and mark the score on a 10cm visual analogue scale (VAS). The overall duration of time patients have been experiencing symptoms will also be recorded.

Baseline blood tests will include full blood count (FBC), Urea and electrolytes (U&E), liver function tests (LFT), C reactive protein (CRP), lactate dehydrogenase (LDH), total protein, and random glucose. . If the participant has an indwelling pleural catheter in situ, drainage diaries will be reviewed and a sample of pleural fluid will be aspirated. Pleural fluid will be tested for protein, LDH, glucose and cytology. If the participant has an effusion that requires aspiration on clinical grounds, a sample of their fluid will be analysed for research purposes. Additional samples of blood and pleural fluid will be processed and stored for use in future research (see Section 6.7).

Participants will be asked to give consent for the research team to access the biopsy on which the diagnosis of mesothelioma was made. If there is sufficient tissue in the biopsy that is surplus to diagnostic or therapeutic requirements, the research team will obtain one or more samples of tissue from the biopsy for research purposes (see Section 6.7)

Thoracic ultrasound (TUS), chest x-ray (CXR) will be performed at baseline. The presence of trapped lung will be recorded. A computed tomography scan (CT) of the thorax should have been performed within 4 weeks of the baseline assessment, ideally with pleural phase contrast, although if a non-contrast scan has been performed within 4 weeks of the baseline assessment, this will suffice.

Eligible participants identified at PICs will be asked to attend one of the study centres on at least one occasion, to provide written or witnessed verbal informed consent and undergo baseline assessment once consent has been provided. In order to reduce inconvenience and increase

study participation, these participants will be offered the opportunity to undergo telephone follow up with reduced data collection, for ongoing study assessments.

6.2 Follow up assessments

Study assessments will be undertaken when the participant attends for review as part of standard clinical care. This should happen every 3 months as a minimum. Some participants will require more frequent follow-up for clinical reasons and will therefore undergo more frequent assessment. Participants who are eligible for participation in future TwiCs may be invited to attend more regular study assessments at one of the study centres, in accordance with the follow up schedule for that specific TwiC.

[figure not shown]
At each visit participants will undergo clinical assessment, including review of symptoms, medication history, oncological treatment received, details of any pain interventions, any engagement with Specialist Palliative Care teams and change in clinical status. Blood tests will be taken for FBC, U&E, LFT, CRP and random glucose,. A sample of blood will be taken for storage. Pleural fluid drainage diaries will be reviewed and documented. Participants who have an indwelling pleural catheter in situ or who are undergoing pleural aspiration for clinical reasons will have pleural fluid biochemistry tested and have a sample of pleural fluid taken for storage. Participants will complete PROMS for QoL and VAS scores for chest pain, breathlessness and sweats. Intermittently participants will be invited to complete daily VAS scores from home and will be provided with a VAS booklet to complete.

Radiological imaging, including CXR, CT thorax and bedside TUS will be undertaken at the discretion of the clinician, based on clinical need. It is anticipated that participants will have a CXR, TUS or both at every clinic appointment as part of routine care. It is expected that participants will have a CT scan every 6 months as a minimum for routine clinical care. If a participant has more frequent CT scans, for clinical reasons, these images will be collected as part of the study.

At each follow up assessment, cohort participants will be assessed for their eligibility to participate in any trials (TwiCs) that are currently underway within the cohort. Any participant who meets the eligibility criteria for a TwiC will be provided with a PIS for that trial and given the opportunity to discuss it with a member of the trial team. As part of the screening process, additional blood samples or investigations may be undertaken to determine or confirm eligibility for specific trials. These activities are deemed ASSESS-meso

Participants in ASSESS-meso who are enrolled in, have completed or are providing control data for a TwiC will undergo adverse event monitoring at each ASSESS-meso visit. This is to ensure ongoing safety monitoring for participants who have participated in CTIMPs, and to allow collection of data on any late-presenting complications.

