3.4 The trial within a cohort design

The trial within a cohort (or ‘Twic’) methodology is a highly pragmatic methodology that aims to remedy certain practical issues seen with the traditional randomised controlled trial (RCT) design.¹⁶

The methodology identifies participants who are eligible for a specific trial from within an existing cohort study. Eligible participants are randomly selected to be offered the trial intervention and are subsequently approached to discuss the trial and invited to consent to participate. Cohort participants who are eligible for the trial but are not allocated to the intervention arm remain in the cohort as controls and are not informed about the intervention.

The Twic methodology offers certain benefits over traditional randomised controlled trial (RCT) design.¹⁶ Cohort studies are associated with faster recruitment and more diverse participant characteristics, which is a benefit in MPM research, where recruitment can be slow and participant diversity narrow.^{12 33}

Twics also offer the following specific advantages for MPM research:

- Chemotherapy has limited efficacy in MPM, and most patients do not receive it.³ Consequently, many people participate in trials in the hope of gaining access to a treatment that is not otherwise available. However, if a trial includes a standard care arm, participants may decline randomisation or withdraw from the trial if allocated to this arm. Alternatively, they may feel disappointed, which could affect patient-reported outcomes. The Twic design removes this issue, and may therefore reduce attrition bias and reporting bias.¹⁶

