- In an RCT, participants are given information about all trial interventions and then randomly allocated to one. This differs from real-life clinical practice where patients are provided with information about treatment as and when they are going to receive it, and not if they are not going to receive it. Twics replicate this by providing information about the intervention solely to participants selected to receive it. This has two benefits: firstly it removes the ethical issue of informing a participant about an intervention that they only have a 50% chance of receiving, and secondly it increases the generalisability of the trial results by replicating real-life clinical care. It also creates a patient-centred consent process, whereby each participant provides consent for the exact treatment they will receive and none that they will not. This aligns well with the culture of open communication that exists between clinicians and patients with MPM.
- The Twic methodology respects patients’ choices to decline treatment. These participants would be excluded from an RCT but can participate in a Twic and contribute observational data to the cohort.

- Using the TwiC design, participants in a cohort can be sampled repeatedly, allowing multiple trials to be undertaken, with shorter recruitment times. If this research demonstrates feasibility, further MPM trials can be undertaken from the same cohort. This could reduce recruitment times, reduce research costs and improve overall efficiency.

The TwiC methodology has been approved by ethics committees for use in intervention trials in patients with breast cancer, rectal cancer and metastatic bone disease³⁴ (see also <https://clinicaltrials.gov/show/NCT02070146>).

It is anticipated that the ASSESS-meso cohort will be used as a resource from which patients with MPM can be identified for future trials, and from which TwiCs will be conducted.

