5.5 Consent for future trials within the cohort

There will be a specific section on the consent form that relates to participation in future TwiCs. This will state “I am willing for my information to be used to identify other research trials that I am eligible for. I am willing to be chosen, on a random basis, to be invited to discuss these trials. I am aware that the decision to participate in future trials will be made at the time of discussion and does not need to be made now”. A further section on the form will ask for participants to give their consent for data collected during ASSESS-meso to be used as control or comparison data for trials, even if they have not been selected to participate in that trial.

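### Section 6.2 gives the trial information sheet to every TwiC-eligible participant, whereas sections 3.4, 5.5 and 8.1 put random selection first and keep unselected controls uninformed

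*Protocol*

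**What the plan says.** Section 6.2 of the protocol (Follow up assessments) sets out what happens at each visit. All cohort participants are checked for eligibility for any TwiC then running, and the next step is: "Any participant who meets the eligibility criteria for a TwiC will be provided with a PIS for that trial". The same sentence offers these people a conversation with the trial team. It depends on eligibility only.

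Section 3.4 (The trial within a cohort design) describes a different sequence: "Eligible participants are randomly selected to be offered the trial intervention and are subsequently approached to discuss the trial and invited to consent to participate". Of eligible people who are not selected, it says that they are "not allocated to the intervention arm remain in the cohort as controls and are not informed about the intervention". It later presents this as a benefit of the design: "Twics replicate this by providing information about the intervention solely to participants selected to receive it".

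The consent statement in section 5.5 follows 3.4. The participant agrees as follows: "I am willing to be chosen, on a random basis, to be invited to discuss these trials". Section 8.1 likewise tells participants that random selection may lead to an invitation, and it makes anyone who has not agreed to this ineligible for TwiCs. The scientific abstract (2.2) also has random selection among eligible participants, with cohort data from the others used as control data.

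**The concern.** Section 6.2 is the procedure that site staff carry out; 3.4 explains why the design was chosen. If the two differ, staff will probably follow 6.2.

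What is at stake is the feature on which the protocol bases its case for TwiCs. Section 3.4 argues that patients who know of a new treatment and are allocated to standard care may refuse, withdraw or be disappointed, and that disappointment could affect patient-reported outcomes. A TwiC is said to avoid this because controls never hear of the intervention. Section 3.4 adds an ethical argument on the same ground: nobody is told about a treatment they may not be offered. Both arguments fail for any control who has been handed the information sheet, and that disclosure cannot be taken back.

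This is not peripheral to the study. Section 4 makes a resource for future TwiCs part of the aim, and section 5.7 counts it among the primary aims.

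**Working it through.** No arithmetic applies, because the point rests on no figure. The check sets the sections side by side and asks two things of each: what must happen before a participant is informed or invited, and what eligible unselected people are told.

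| Protocol section | Condition for being informed or invited | Eligible but not selected |
|---|---|---|
| 2.2 Scientific abstract | Random selection of a proportion of eligible participants to receive the intervention | Their ongoing cohort data serve as control data |
| 3.4 TwiC design | Eligibility, then random selection, then approach | Controls, not informed |
| 5.5 Consent | Random choice, then invitation to discuss | Data may be used as control data, under a separate consent item |
| 6.2 Follow-up | Eligibility only | Not distinguished; would receive the information sheet |
| 8.1 Ethics | Random selection, then invitation; people who refuse this item are not eligible | Not addressed |

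1. Could 6.2 be read as consistent with 3.4? Only if meeting a TwiC's eligibility criteria already included having been selected. Section 3.4 rules this out: it selects from among eligible people and defines controls as eligible people who were not allocated to the intervention.
2. Does other text restrict 6.2? No text available for review limits the instruction to selected participants.
3. What follows from the literal text? Every eligible participant receives the information sheet. Controls are by definition eligible, so every future control seen at such a visit would be informed, where 3.4 requires that none be.
4. What does not change? Section 6.2 does not cancel random selection, which 2.2, 3.4, 5.5 and 8.1 all retain. The cohort's sample size (5.6) and its planned analyses (section 7) do not depend on who is told about a TwiC.

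**The case against.** The strongest reply is that the chosen design is clear from several other sections and that 6.2 merely omits a few words about selection. Section 6.2 also refers to an information sheet, a trial team and a follow-up schedule belonging to each TwiC, so trial-specific documents are evidently expected and could set the right order. The study flow diagram is not visible in the text reviewed, and the relevant paragraph of 6.2 breaks off before its end, so a selection step may be shown elsewhere.

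Part of this stands. The intended design is not in doubt, so the defect is an inconsistency and not a wrong choice of design. It also cannot be claimed that sites are given no selection step anywhere. But neither a diagram nor missing text would make the quoted sentence correct. The protocol does not say that a TwiC's own documents override 6.2, so a TwiC protocol with the right order would conflict with this one until 6.2 is changed. The plain-English summary (2.1) says that invitation is only sometimes by random selection. That may cover trials of other kinds, whereas 6.2 names TwiCs.

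A reader might go further in three ways that the documents do not support:

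- **The randomised comparison is lost, with people who decline becoming the controls.** No section makes decliners the control group. Section 3.4 says only that they can contribute observational data to the cohort. If selection still takes place, the comparison remains randomised and what is lost is the uninformed control group.
- **People who refused random selection but allowed control use could be counted as controls.** Section 8.1 makes them ineligible for TwiCs, and 3.4 draws controls from eligible people.
- **A given increase in a TwiC's sample size follows.** The protocol specifies no TwiC and gives no rate at which informed controls would withdraw or seek similar treatment elsewhere. Those two behaviours also act differently: one loses data, the other dilutes the effect.

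**Conclusion.** The contradiction is real and should be fixed. Section 6.2 makes eligibility the sole trigger for giving out the trial information sheet, against the design description in 3.4 and the order of events in 5.5 and 8.1.

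Its size can be stated only in kind: under the literal text all eligible controls are informed, where the design requires that none be. The consequence is loss of the claimed protection against disappointment, attrition and reporting bias in any embedded trial. This assumes that sites follow 6.2 as written and that the TwiC's own documents do not correct the order. The consequence does not extend to the validity of random selection itself, nor to the cohort's observational objectives.

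**What to change.** Replace the sentence in 6.2 with text to this effect: eligible participants who have given the TwiC consents in section 5.5 enter the random selection for that trial; only those selected are given its information sheet and approached; those eligible but not selected are not informed and serve as controls. Requiring both consent items before selection means that everyone who enters it can be used in either group. Check that the flow diagram shows the same order.

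The analysis rule for people who are selected and then decline belongs in each TwiC's own protocol and need not be settled here.

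The cost is a few sentences in an amendment and a note to sites, with no extra data or participants. It should be in place before sites apply 6.2 to any TwiC.
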